Investigating the role of nebulised mucolytic therapy during lower respiratory tract infections post lung transplantation

Clinical Protocol

Background

According to the International Society for Heart and Lung Transplantation (ISHLT), the incidence of lung transplants per annum worldwide is rising annually, with over 3000 transplants completed according to the latest registry¹⁰. The Alfred is a state-wide, internationally renowned lung transplant service, transplanting between 59 - 79 patients over the last two calendar years, with a waitlist of more than 40 potential recipients. This makes it one of only 7 centres worldwide completing this volume of transplants¹⁰.

Patients who have undergone lung transplantation for end-stage lung disease are subject to life-long immunosuppression to prevent allograft rejection. These patients are at a heightened risk of acquiring opportunistic lower respiratory tract infections (LRTI)¹³, often characterised by sputum retention and / or production, which can have a negative impact on both morbidity and mortality¹¹. Patients post lung transplant often find it difficult to clear secretions due to an alteration in normal physiology. Transplanted lung tissue is denervated upon resection from the donor, which has been shown to lead to slower ciliary beat frequencies¹², impaired muco-ciliary clearance (MCC) rates¹²⁻¹⁴ and an impaired cough reflex²⁵. Devascularisation to lung tissue post ischaemic surgical time in the acute period can lead to an alteration in mucosal properties and structural changes around anastomoses, which may further impair the ability to clear secretions¹¹.

Inhaled, nebulised mucolytic agents are commonly used in the management of other suppurative chronic lung diseases characterised by excessive production of secretions. Dornase alfa acts by digesting the extracellular DNA released by inflammatory cells during infection⁸. It has been shown to have positive long-term effects on lung function in cystic fibrosis (CF)⁸ and short-term benefits treating atelectasis and mucous plugging in acute, non-CF adult and paediatric cases³⁻⁵. Yet shown to be safe in normal subjects⁸, it has been shown to have a detrimental effect on pulmonary function in non-CF bronchiectasis¹⁷.

Inhaled saline acts by restoring the airway surface liquid layer of the mucosa, favourably altering mucous properties, accelerating MCC and stimulating cough¹⁻². Positive evidence exists for hypertonic saline (6-7%) in CF¹⁻² and both hypertonic and isotonic (0.9%) saline in non-CF bronchiectasis⁶. There is discussion of clinical use of saline as a mucolytic in the post transplant patient⁹ with no evidence by way of randomised controlled trial to demonstrate effect. There is no current evidence on the use of inhaled mucolytics post transplant.

Currently, both dornase alfa and saline (isotonic / hypertonic) are used in the inpatient and outpatient setting at this institution as a reactive treatment strategy for LRTI characterised by excessive sputum production and / or retention. We believe this warrants a short-term, randomised trial to assess the efficacy of current practice, and to evaluate whether dornase alpha is more effective than 0.9% saline, a cheaper, more accessible alternative.

Aim

To evaluate the efficacy of inhaled dornase alfa compared to inhaled isotonic (0.9%) saline on:

- Quantitative and qualitative respiratory outcomes
- The need for antibiotics, length of stay and exacerbation / re-admission rates

Hypothesis

Dornase alfa is more effective than isotonic saline in the post lung transplant population during LRTI.

Study design

Phase 2, assessor blinded, prospective randomised controlled trial.

Study population

Inclusion:

- Post bilateral sequential lung transplant
- Capable of performing airway clearance techniques / nebulisers
- Pulmonary exacerbation as defined by Fuchs et al⁸
- Must be productive of sputum

*As part of the Fuchs criteria screening, existing plain film CXR or CT scans taken as part of standard care will be used based on availability and the fulfilment of other criteria points to assess patient suitability.

Exclusion:

- Paediatric transplant <18yrs
 - Single lung transplant – native lung physiology may confound outcome measures
 - Interstate – unable to complete follow up
 - Unable to perform lung function testing
 - Unable to complete subjective outcome measures- unable to read English fluently
 - Critically unwell / ICU / ventilator dependent
 - Within 2 months of transplant date
- *Cystic Fibrosis will be stratified

Intervention

On admission to the ward as an inpatient, patients who give informed consent will be randomly assigned to one of two groups defined below. The randomisation sequence will be concealed using opaque envelopes. Randomisation will be stratified according to pre-transplant diagnosis (cystic fibrosis or not) as people with cystic fibrosis are expected to be younger and have a different underlying systemic disease process.

Treatment group: Once daily, 2.5ml inhaled dornase alfa (evening if able) with inhalational breathing routine (IBR). IBR consists of 4 slow deep breaths followed by 6 relaxed breaths, repeated until nebuliser is complete, coughing when the patient feels the need to expectorate. The patient will be instructed to sit in an upright position with upper limb support as able.

Control group: Once daily, 5ml inhaled 0.9% normal saline with IBR as above (evening if able).

All participants will undertake treatment for one month according to their allocated group, with follow up to 3 months, (2 months off randomised intervention). Both groups will continue to do their regular prescribed physical exercise routine over the course of the study.

Timing of assessment

All outcome measures will be performed at study baseline, 1 month and 3 months follow-up. Daily outcome measures used as a monitoring diary are an exception. There are no cough-specific quality of life questionnaires validated for use in the post lung transplant population.

Primary outcome

Lung clearance index (LCI) is a measure of ventilation inhomogeneity as measured during multiple breath washout (MBW) of inert tracer gases. It has been shown that this test is a potentially more sensitive measure of peripheral airway obstruction than regular spirometry in short term (4 week) mucolytic interventional studies in paediatric CF^{18,19}. This test would be performed within the respiratory physiology lung function laboratory on site at all assessment points, by an assessor who is blinded to group allocation for follow up data collection.

Conventionally used primary endpoints in this population, such as regular spirometry¹¹, may be unable to detect between group differences without large sample sizes and long treatment durations. Based on current evidence from non-lung transplant populations, LCI has been able to show short-term change, whereas regular spirometry has not shown change^{18,19}.

Secondary outcomes – to be completed at specified follow up times as above

1. Regular spirometry (FEV1, FVC, FEF)
2. Cough specific quality of life (QOL)
 - Leicester Cough Questionnaire (LCQ)²⁴
 - St. George's Respiratory Questionnaire (SGRQ)²³The LCQ is a 19-question tool, the SGRQ a 2-part questionnaire, both are validated QOL questionnaires used in chronic lung disease other than lung transplant
3. Inpatient days
4. Oral, inhaled or IVAB days (for LRTI only)
5. Number of hospitalisations
6. Exacerbations over study period – as defined by:
 - Presentation to hospital and commencement of antibiotics (oral, inhaled or IV)
 - Worsening of symptom scores (BCSS >1²⁰), sputum colour score (BronkoTest colour 3-5)
7. C-reactive protein (CRP). An inflammatory marker measured with routine blood tests on admission with LRTI. Taken during IP stay and routinely on OP follow-up. Existing / available data only will be used – no extra routine bloods will be taken on account of study inclusion.

Secondary outcomes – to be completed daily

8. Self-reported symptom severity, used as a daily patient diary
 - Breathlessness, Cough and Sputum Scale (BCSS)²⁰The BCSS is a 12 point self-reported symptom severity score, validated for daily use in COPD
 - Sputum colour score²² – BronkoTest Ltd, London UKSputum colour has been shown to correlate with physiological infection in other chronic lung disease groups.
 - Sputum quantity (nil, low, moderate, high)Self-reported symptom scores are to be completed at the same time each day, prior to going to bed. They will be collected at each assessment interval as above. Treatment compliance will be measured by return of used and un-used medication packaging at each assessment point.

Sample size and power calculation

A total of 30 participants (15 in each group) will enter this design study. The probability is 80 percent that the study will detect a treatment difference at a two-sided 0.05 significance level, if the true difference between treatments is 1.000 unit in LCI.

This is a conservative estimate that is smaller than previous differences found in paediatric populations^{18,19}. This is based on the assumption that the standard deviation of the response variable is 0.94 units^{18,19}.

As a phase 2 study, this project is powered to detect differences in physiological outcomes, rather than quality of life or hospitalization. However, should the treatment prove to have physiological benefits, the secondary outcomes of this study will provide critical information for powering a future phase 3 trial.

Feasibility: Approximately 12 patients with pulmonary exacerbations are admitted under the lung transplant service each month (minimum estimate). We estimate that 70% will meet the eligibility criteria for the study and 50% will consent to participate. We therefore anticipate that it will be possible to recruit the numbers needed for this study in 8 months.

Statistical analysis

An intention to treat analysis will be conducted, with inclusion of all randomised participants, regardless of study completion. Data for continuous outcomes including LCI will be analysed using a linear mixed models analysis, which makes use of all available data at each time point and is less affected by incomplete data than analysis of variance. The likelihood of exacerbation or hospitalisation during the follow-up period for the dornase alpha group will be expressed as a relative risk compared to the isotonic saline group.

Bias / Confounders

There is potential for performance bias in this study due to the lack of ability to blind participants to their allocated treatment regimen. We are unable to package medications in a way other than that currently produced. We aim to outline, as part of the PICF, that both inhaled medications have proven to be efficacious (and detrimental in certain circumstances) in disease processes other than post lung transplant LRTI. Detection bias will be controlled by the use of a blinded outcome assessor for all follow-up data collection points.

Potential confounders in this study include the diagnosis of bronchiolitis obliterans (BOS), or chronic lung rejection, during which LRTI occurs simultaneously. Patients with a diagnosis of BOS may in fact demonstrate differences in lung physiology and ease of sputum expectoration, which may have an effect on outcomes variables. We feel that excluding these patients may have a detrimental impact on the external validity of this study, therefore we will stratify patients according to a diagnosis of BOS on study inclusion.

Outcomes and significance

This will be the first randomised controlled trial to analyse inhaled dornase alfa and isotonic saline in the post lung transplant population.

The outcome of this trial will help to guide physiotherapy and pharmacological management of post lung transplant patients with LRTI in the future, both nationally and internationally.

References

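### The exacerbation outcome has no new-event rule although everyone enters with an exacerbation, so its relative risk can mix slow resolution of the index infection with new events

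*Combined protocol and SAP*

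**What the plan says.** The Study population section requires a current pulmonary exacerbation at entry and adds "Must be productive of sputum". The Intervention section sets the time of randomisation: "On admission to the ward as an inpatient, patients who give informed consent will be randomly assigned to one of two groups defined below". Treatment lasts one month and follow-up runs to three months.

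Among the secondary outcomes, item 3 is inpatient days, item 5 is the number of hospitalisations, and item 6 is exacerbations across the study period. Item 6 has two bullets. The first is a hospital presentation with antibiotics being started. The second is "Worsening of symptom scores (BCSS >1²⁰), sputum colour score (BronkoTest colour 3-5". No word joins the two bullets, or the two parts of the second. BCSS and sputum colour are self-reported in a daily diary (item 8).

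The Statistical analysis section gives the summary measure: "The likelihood of exacerbation or hospitalisation during the follow-up period for the dornase alpha group will be expressed as a relative risk", with saline as the comparator. The Aim names "The need for antibiotics, length of stay and exacerbation / re-admission rates".

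No section says when the event window opens, whether the index admission counts, what BCSS is compared with, or whether the index episode must end before another event can be counted.

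**The concern.** Everyone has, at time zero, the condition that is later counted as an outcome. Without a rule that separates the index episode from a new one, the definition can fail in two directions.

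- **Counting a non-event.** Sputum colour 3-5 is a level, not a change. A participant whose index infection is still producing coloured sputum in the first diary days can meet it without any new exacerbation.
- **Missing an event.** If BCSS is compared with the admission value, when symptoms are likely to be near their worst, a participant can relapse and still score below the reference.

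The relative risk would then blend two questions: how fast the index infection clears, and how often a new one occurs. The Sample size section says that the secondary outcomes will help to power a phase 3 trial, so a blended event rate would carry over into that design. Participants are unblinded (Bias / Confounders) and the diary is self-reported, which is a further reason to settle the rule before outcome data are seen.

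**Working it through.** **1. The plan's own figure.** The only power calculation is for the lung clearance index (LCI): difference 1.0, SD 0.94, two-sided 0.05, 80% power, 15 per arm. Normal approximation: n per arm = 2 × (1.960 + 0.842)² × 0.94² / 1.0² = 13.9, so 14 per arm and 28 in total. Exact t-based power at 15 per arm is 0.803. The stated 30 participants reproduce. This does not bear on item 6, for which the plan gives no event rate.

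**2. Inputs for the illustration (all assumed).** True new-exacerbation risk p0 = 40% on saline and p1 = 20% on dornase alfa, so the true relative risk (RR) is 0.50. Let q be the share of an arm counted as an event because of the index infection, taken as independent of new-event risk within the arm.

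**3. Equal carry-over.** Observed RR = [q + (1 − q)p1] / [q + (1 − q)p0].

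| q in both arms | dornase alfa | saline | observed RR |
|---|---|---|---|
| 0 | 0.20 | 0.40 | 0.50 |
| 0.10 | 0.28 | 0.46 | 0.61 |
| 0.25 | 0.40 | 0.55 | 0.73 |
| 0.50 | 0.60 | 0.70 | 0.86 |
| 0.75 | 0.80 | 0.85 | 0.94 |
| 1.00 | 1.00 | 1.00 | 1.00 |

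At q = 0.50, with saline risk from 30% to 60% and true RR 0.50, the observed RR runs from 0.575/0.650 = 0.88 to 0.650/0.800 = 0.81. The saline rate passed to phase 3 planning also changes: at q = 0.50 a true 40% would read as 70%.

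**4. Unequal carry-over.** Resolution of the index infection happens after randomisation and may depend on treatment, so q need not be equal.

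- q = 50% saline, 10% dornase alfa: (0.10 + 0.90 × 0.20) / (0.50 + 0.50 × 0.40) = 0.28/0.70 = 0.40.
- q = 25% saline, 50% dornase alfa: (0.50 + 0.50 × 0.20) / (0.25 + 0.75 × 0.40) = 0.60/0.55 = 1.09.

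The bias can therefore go either way.

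**5. The BCSS reference.** Take a participant who scores 9 at admission, recovers to 3 and relapses to 7. Against admission the change is 7 − 9 = −2, which is no worsening. Against the recent level it is 7 − 3 = +4, which exceeds 1. The same diary gives opposite answers.

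**6. Hospitalisations.** If the index admission were counted, both arms would be 15/15 and the RR exactly 1. As a count, assumed means of 0.4 and 0.2 would become 1.4 and 1.2: the ratio moves from 0.50 to 0.86, while the difference stays at −0.2.

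**7. Precision.** Even undiluted, 40% versus 20% with 15 per arm has low power. The standard error is √(2 × 0.3 × 0.7/15) = 0.167 under the null and √((0.24 + 0.16)/15) = 0.163 under the alternative. Then (0.20 − 1.96 × 0.167)/0.163 = −0.78, a power of about 22%.

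**The case against.** The strongest reply is that the plan is loosely worded but does not set out to count the index event. The Aim speaks of re-admission. The first bullet of item 6 needs antibiotics to be started. The relative risk covers the follow-up period. The index presentation comes before randomisation. All of this favours a new-events reading, most clearly for hospitalisation. That stands: a reader might infer that hospitalisation will be 15/15 in both arms, but the text does not support this as the likely reading. What is missing is a counting rule.

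Second, the two bullets may be joint requirements, and worsening may govern sputum colour as well as BCSS. On either reading, persistent index colour alone triggers nothing. That also stands, and it is why the counting problem is conditional on the criteria being separable. Likewise, no section says that BCSS is compared with admission; in a daily diary, comparison with recent days is equally open.

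Third, a reader might infer that the relative risk must move towards 1. That needs equal carry-over, which nothing in the plan secures (step 4).

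Fourth, inpatient days (item 3) are not analysed as a relative risk, and length of stay is a stated aim, so index days belong in that outcome. They need separate reporting, not removal.

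Finally, it is tempting to start the clock only once the index episode has resolved. That would make time zero a post-randomisation event that treatment may affect, and would drop non-resolvers from an analysis that the plan says includes all randomised participants.

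**Conclusion.** The concern holds as a gap in the definition of item 6, with conditional consequences. If the criteria can be met separately, the unresolved index infection can be counted as an outcome event; if BCSS is judged against admission, a relapse can be missed. The relative risk is then diluted towards 1 under equal carry-over (0.50 to 0.86 at 50%, for assumed risks of 40% and 20%) and distorted in either direction otherwise (0.40 or 1.09 in the examples). Every rate here is an assumption; the omissions themselves can be read directly from the plan.

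A reader might go further and conclude that the trial cannot address its exacerbation and re-admission aim. The documents do not support that, because the diary, antibiotic days and hospitalisations are already to be collected and only the counting rule is missing. The outcomes are secondary, and the Sample size section says that the trial is powered for physiological outcomes and not for hospitalisation. This is a should-fix, and the primary LCI analysis is unaffected.

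**What to change.** Before any outcome data are examined, amend items 3, 5 and 6 and the Statistical analysis section as follows.

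1. In the number of hospitalisations and its relative risk, count only admissions after index discharge. Report index length of stay from randomisation separately from readmission days, and keep both.
2. State the and/or logic of item 6. Count an exacerbation only when it is a new event, and define what makes it new. Judge BCSS and sputum colour as worsening from the participant's own recent diary level, over a prespecified window, instead of from the admission value or an absolute colour.
3. Keep all randomised participants in the denominator from randomisation. Report non-resolution of the index episode separately by arm, to be read alongside the new-event relative risk, without removing those participants.
4. Show events separately for the treatment month and the two off-treatment months.

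The cost is outcome-definition and analysis wording; no new data are needed. There will be fewer counted events in month 1, and a recent-diary reference can miss a gradual decline, so the choice of window should be justified.

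### The LCI mixed model names no baseline adjustment, no CF term and no visit for the primary comparison; all three should be fixed in advance

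*Combined protocol and SAP*

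**What the plan says.** The Statistical analysis section states: "Data for continuous outcomes including LCI will be analysed using a linear mixed models analysis". It recommends this model as one "which makes use of all available data at each time point". No fixed effects, covariance structure, degrees-of-freedom method or test contrast follow.

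Other sections supply the design facts that the model would need:

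- Timing of assessment: "All outcome measures will be performed at study baseline, 1 month and 3 months follow-up".
- Intervention: one month of allocated treatment, "with follow up to 3 months, (2 months off randomised intervention").
- Intervention, on allocation: "Randomisation will be stratified according to pre-transplant diagnosis (cystic fibrosis or not"). The Study population section agrees: "Cystic Fibrosis will be stratified".
- Bias / Confounders: "Patients with a diagnosis of BOS may in fact demonstrate differences in lung physiology and ease of sputum expectoration". For that reason patients are to be stratified by BOS at inclusion. The randomisation text under Intervention does not mention BOS.
- Primary outcome: LCI is justified by "short term (4 week) mucolytic interventional studies in paediatric CF", but no visit is named. The Sample size and power calculation section names none either.

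**The concern.** Baseline LCI will already have been collected, and CF is built into the randomisation, yet the stated analysis uses neither. If baseline LCI predicts follow-up LCI, leaving it out wastes information in a trial of 30 people. If CF predicts LCI and allocation is balanced on it, leaving CF out makes the standard error too large: the test rejects less often than 5% under no effect and has less power than it could.

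The two follow-up visits also answer different questions. One month shows the effect at the end of treatment; 3 months shows what remains two months after it stops. With no visit named, the one comparison the trial is powered for is not uniquely defined, and the choice could be made after the data are seen.

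**Working it through.** **Inputs from the protocol** (Sample size and power calculation): 15 per arm, true difference 1.000 LCI unit, SD 0.94, two-sided 0.05. The text does not say whether 0.94 is the SD at a visit or of a change. **Assumed, because the documents are silent:** the baseline-to-follow-up correlation r, the persistence of the effect, and the prevalence and prognostic strength of CF and BOS. A baseline taken during an exacerbation would lower r; stable differences between patients would raise it.

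**1. The plan's own figure.** SE = 0.94 × √(2/15) = 0.343. Noncentrality = 1.000/0.343 = 2.913. With t on 28 df (critical value 2.048), power is 80.3%; at 14 per arm it is 77.3%. The stated 15 per arm is reproduced.

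**2. Baseline handling at one visit, 0.94 as the SD at a visit.** Change-score SD = 0.94 × √(2 − 2r), 28 df. Baseline-adjusted SD = 0.94 × √(1 − r²), 27 df, with the SE multiplied by √(28/27) for chance baseline imbalance.

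| r | Ignoring baseline | Change score | Baseline-adjusted |
|---|---|---|---|
| 0 | 80.3% | 51.2% | 78.8% |
| 0.1 | 80.3% | 55.4% | 79.2% |
| 0.2 | 80.3% | 60.4% | 80.4% |
| 0.3 | 80.3% | 66.2% | 82.4% |
| 0.5 | 80.3% | 80.3% | 89.0% |
| 0.7 | 80.3% | 95.2% | 97.1% |

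If 0.94 is instead the SD of change, the SD at a visit is 0.94/√(2 − 2r) = 0.794, 0.940 and 1.214 at r = 0.3, 0.5 and 0.7. Power is then 80.3% for change, 92.8, 89.0 and 84.9% adjusted, and 91.4, 80.3 and 58.7% ignoring baseline.

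**3. The CF term.** Simulation of one visit (40,000 trials), baseline not used, CF balanced between arms, 8 or 14 of the 30 with CF, total SD held at 0.94:

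| Assumed CF effect (LCI units) | Type I error without / with CF | Power without / with CF |
|---|---|---|
| 0 | 4.9–5.0% / 5.0% | 80.0–80.2% / 79.9–80.2% |
| 0.5 | 4.2–4.3% / 4.9–5.1% | 80.9–81.1% / 82.6–83.0% |
| 1.0 | 2.0–2.6% / 4.9% | 82.5–83.3% / 88.6–91.4% |

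Much of this gain is shared with baseline adjustment. A second simulation (9,000 runs per cell) took CF and BOS at 30% each, together explaining 20% of the variance, with only CF in the randomisation. At r = 0.3 and 0.5, type I error was 4.1 and 4.3% with neither baseline nor strata terms, and 4.5 and 4.6% with baseline alone. Adding both strata terms to the baseline-adjusted model raised power from 82.4 to 85.4% and from 89.7 to 90.3%.

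**4. The visit.** The baseline-adjusted average of both visits, with equal correlations, has variance 0.94² × ((1 + r)/2 − r²). At r = 0.3, 0.5 and 0.7:

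- effect fully persisting: average 95.8, 97.4 and 99.6%, against 82.4, 89.0 and 97.1% at 1 month alone (13.4, 8.4 and 2.5 points in favour of averaging);
- effect gone by 3 months (mean effect 0.5): average 45.4, 49.6 and 63.3%, against the same 1-month figures.

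With no true effect, counting a significant result at either visit gives a type I error of 8.4 to 9.3% (raw or change scores, r = 0.5 and 0.7).

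**5. The cost of a BOS term that is not needed.** With CF balanced by blocks, BOS (30% prevalence) left to chance and neither prognostic, a model with both terms has average power of about 78% and a 5th percentile of about 74%, against 80.3% without them.

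**The case against.** The plan omits detail; it does not state a wrong model. A linear mixed model with baseline as one of its time points is compatible with full baseline adjustment. One month is also strongly implied, by the length of treatment and by the 4-week studies cited. Every gain above depends on correlations and stratum effects that the documents do not give; at r = 0.3 the gain over ignoring baseline is only 2 points, and at 0.1 it is a small loss. All of this stands. It limits the size of the point but not its substance: an implied visit is not a specified one, and the wording allows analyses with clearly different power.

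A reader might infer more than the documents support:

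- *That the plan uses a change score, or averages the visits.* It says neither. The 66% and 45% figures describe what those choices would do, not what is planned.
- *That the type I error is inflated.* A three-visit model of this kind tested against a normal reference gave about 7% in simulation, but the plan states no reference distribution. This is a reason to name a small-sample method, not a fault found. The omitted CF term errs in the conservative direction.
- *That the trial is too small or its estimate biased.* The sample size reproduces, and randomisation protects the unadjusted estimate.
- *That only one model will do.* A baseline covariate and a common baseline mean are both adequate. The power of a full constrained model with Kenward-Roger was not evaluated here.

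**Conclusion.** The point holds as a gap that should be closed before the data are seen. The LCI analysis specifies neither baseline LCI nor the CF stratum, and no primary visit. With 0.94 as the SD at one visit and r assumed at 0.3, 0.5 and 0.7, baseline adjustment adds about 2, 9 and 17 points to the 80.3% obtained by ignoring baseline. It beats a change score at each of these values under either reading of 0.94. The gain disappears below r of about 0.2. Leaving out a prognostic CF stratum makes the test conservative, by an amount that depends on a CF effect the documents do not give. Which visit matters more for power depends on persistence, which is unknown; the case for 1 month rests on the treatment period and the cited precedents. Whether BOS is a randomisation stratum is unresolved between Intervention and Bias / Confounders.

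**What to change.** In the Statistical analysis section, state that the LCI mixed model:

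- adjusts for baseline LCI, as a covariate or through a baseline mean common to both arms;
- includes CF as a fixed effect;
- includes group-by-visit terms;
- uses a small-sample degrees-of-freedom method such as Kenward-Roger;
- takes the between-group difference at 1 month as the primary contrast and that at 3 months as secondary.

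Reconcile Intervention with Bias / Confounders on BOS. If BOS is a randomisation stratum, include it as a covariate. If it is not, including it is optional, since an unbalanced, non-prognostic term can cost several points of power.

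The cost is a few sentences, with no new data and no extra participants. In power, it is about 1.5 points if baseline is uncorrelated with follow-up, about 0.1 to 0.2 points for a balanced CF term that is not prognostic, and about 13, 8 and 2 to 3 points (r = 0.3, 0.5, 0.7) against averaging both visits if the effect fully persists to 3 months.

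### The claim that a blinded assessor controls detection bias does not hold for participant-scored outcomes; separately, the yes/no relative risk leaves repeat events out of an aim stated in rates

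*Combined protocol and SAP*

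**What the plan says.** All places are in the combined protocol and SAP.

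- **Bias / Confounders.** The plan admits a "lack of ability to blind participants to their allocated treatment regimen", treats this as a source of performance bias, and then states "Detection bias will be controlled by the use of a blinded outcome assessor for all follow-up data collection points". The sentence carries no limit to particular outcomes.
- **Primary outcome.** The blinded assessor is described once, for LCI, which is measured in the lung function laboratory "by an assessor who is blinded to group allocation for follow up data collection".
- **Secondary outcomes, item 2.** LCQ and SGRQ are questionnaires. The exclusion criteria remove patients who cannot complete the subjective measures because they do not read English fluently, so the participant fills them in.
- **Secondary outcomes, item 8.** BCSS, sputum colour and sputum quantity are "Self-reported symptom severity, used as a daily patient diary".
- **Secondary outcomes, item 6.** Exacerbation has two limbs. One is "Presentation to hospital and commencement of antibiotics (oral, inhaled or IV"). The other begins "Worsening of symptom scores" and uses BCSS and sputum colour.
- **Secondary outcomes, item 7.** CRP comes only from existing routine blood tests.
- **Aim, item 5 and Statistical analysis.** The aim refers to rates of exacerbation and re-admission, and item 5 is a number of hospitalisations. The one event analysis given is the likelihood of exacerbation or hospitalisation, expressed as a relative risk. The linear mixed model is assigned to continuous outcomes.

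**The concern.** Detection bias arises where an outcome is rated. A blinded person who collects a completed form does not blind the rating on it. For the questionnaires and the diary the rater is a participant who knows the allocation, so the design lacks the property that the sentence claims. BCSS and sputum colour also feed the exacerbation definition. The other limb of that definition depends on decisions to admit and to start antibiotics, and the plan describes no blinding of the clinicians who make them.

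The second matter is one of fit. A yes/no summary counts a patient with three events the same as a patient with one, and no analysis is named for the count in item 5. The sample size section says the secondary outcomes should inform a phase 3 trial if a physiological benefit is shown. An event rate with its uncertainty is useful for that purpose, and the stated analysis does not produce one.

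**Working it through.** **Step 1. Who makes each rating**

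| Outcome | Rated or generated by | Blinding described? |
|---|---|---|
| LCI | laboratory assessor | yes, at follow-up |
| Spirometry | not named | only if the same assessor performs it |
| LCQ, SGRQ | participant | no |
| BCSS, sputum colour, sputum quantity | participant | no |
| Exacerbation, symptom limb | participant scores | no |
| Exacerbation, hospital limb; admissions; antibiotic starts | treating clinicians | none described |
| CRP | routine care | not collected by the study assessor |

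The unqualified sentence is supported for the first row, possibly for the second, and for no other.

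**Step 2. Possible size of a reporting shift**

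The plan gives no figure on this point. Its 15 per arm is the only input, and it reproduces: for a difference of 1.000 and SD 0.94, a two-sample t-test needs 14.89, so 15 per arm, with power 80.3%.

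Assume no true effect and a between-arm shift of d SD caused by knowledge of allocation. With 28 df, the noncentrality is d × sqrt(15/2):

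- d = 0.25: 0.685, chance of p < 0.05 is 10.1%
- d = 0.50: 1.369, chance of p < 0.05 is 26.2%

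This uses a single time point as a stand-in for the mixed model.

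**Step 3. Relative risk against rate ratio**

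Event rates are assumed, because the documents give none. Take 0.5 v 1.0 events per patient at 15 per arm: 7.5 and 15 expected events, true rate ratio 0.50.

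*No overdispersion (Poisson).*
- Risks: 1 − exp(−0.5) = 0.393 and 1 − exp(−1) = 0.632, so RR = 0.62. SE(log RR) = sqrt(0.607/5.90 + 0.368/9.48) = 0.376, 95% CI 0.30 to 1.30.
- About 15.4 patients have an event against 22.5 events, so 1 − 15.4/22.5 = 32% of events are not used.
- Rate ratio: SE = sqrt(1/7.5 + 1/15) = 0.447. With t(28) = 2.048 the interval is 0.50 × exp(±0.916) = 0.20 to 1.25.
- Log effect over SE: 0.693/0.447 = 1.55 for the rate ratio, 0.475/0.376 = 1.26 for the RR.

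*Overdispersion (negative binomial, dispersion 1).*
- Risks m/(1 + m) = 0.333 and 0.500, RR = 0.67, SE = sqrt(0.667/5 + 0.5/7.5) = 0.447, CI 0.28 to 1.60. Events not used: 1 − 12.5/22.5 = 44%.
- Rate ratio: expected Pearson dispersion (1.5 + 2.0)/2 = 1.75. SE = 0.447 × sqrt(1.75) = 0.592, and 0.50 × exp(±2.048 × 0.592) = **0.15 to 1.68**.
- Log effect over SE: 0.693/0.592 = 1.17 against 0.405/0.447 = 0.91.

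*Range.*
- 1.0 v 2.0, dispersion 1: dispersion (2 + 3)/2 = 2.5, SE = 0.316 × sqrt(2.5) = 0.500, interval 0.18 to 1.39.
- 0.25 v 0.5, Poisson: log effect over SE is 0.693/0.632 = 1.10 against 0.576/0.581 = 0.99, so almost nothing is gained. The lower arm has no event in exp(−3.75) = 2.3% of trials, and the ratio then cannot be estimated.

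**Step 4. Why estimate the dispersion**

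In 40,000 simulated trials at 0.5 v 1.0, with dispersion 0 / 0.5 / 1, coverage of a nominal 95% interval was 96.4% / 92.9% / 89.5% for plain Poisson. With estimated dispersion and t on 28 df it was 96.3% / 96.5% / 96.7%.

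**The case against.** The plan does not hide the open design. The paragraph that makes the claim begins by admitting that participants are unblinded, the study design section claims only assessor blinding, and the diary is labelled self-reported. The phrase about collection points may also mean the 1- and 3-month visits, since the Timing of assessment section treats the daily measures as an exception. These points soften the harm. They do not rescue the sentence, because LCQ and SGRQ are completed at those visits by unblinded participants. The planned consent wording, that both agents have helped in other diseases, may temper expectations but masks nobody.

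On events, a re-admission rate is often reported as a proportion, and the number of hospitalisations is collected anyway. This stands. A reader might infer that the relative risk fails to measure what the aim names, but that is too strong: it answers a legitimate question and leaves out repeat events.

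Two other inferences are tempting and unsupported. The first is that the primary outcome is unblinded in practice. Packaging is returned at each assessment point ("Treatment compliance will be measured by return of used and un-used medication packaging at each assessment point") and cannot be disguised ("We are unable to package medications in a way other than that currently produced"), but nothing says that the LCI assessor receives it. The second is that the hospital limb should become the main exacerbation definition. The plan does not say how the limbs combine, and the hospital limb is itself open to knowledge of allocation.

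**Conclusion.** The detection-bias sentence is wrong as written for LCQ, SGRQ, BCSS, sputum colour, sputum quantity and the symptom limb of exacerbation. This follows from the text alone and needs no assumption. Its numerical effect is unknown; the 10% and 26% false-positive figures rest on assumed shifts of 0.25 and 0.5 SD.

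The lack of a rate analysis is a cheap improvement to make, not an error. All the event rates are assumptions, the gain over the relative risk is modest at best and very small when events are few, and none of the overdispersed intervals shown excludes 1.

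Only secondary outcomes, which the plan says it is not powered for, are touched. The LCI conclusion is unaffected. The packaging point is an optional safeguard, and the missing references for the BCSS change and the colour range are minor clarifications.

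**What to change.** 1. **Bias / Confounders.** Limit the sentence to LCI, and to spirometry if the same blinded laboratory assessor performs it. Leave CRP out. State that LCQ, SGRQ, BCSS, sputum colour and sputum quantity are unblinded participant reports, and report them as such. Acknowledge that admissions and antibiotic starts may be influenced by knowledge of allocation.
2. **Item 6.** State how the two limbs combine and report events meeting each limb separately, without ranking one above the other. In the same edit, give the reference against which BCSS and sputum colour are judged.
3. **Statistical analysis.** Keep the relative risk. Add event counts per arm and a descriptive rate ratio for events after randomisation, excluding the index admission. Use a Poisson model with log follow-up time as offset, dispersion estimated from the data, and a t-based interval on the model's residual degrees of freedom. That is 28 only if no stratification factor is included; main effects for cystic fibrosis and BOS would give 30 − 4 = 26. Say that the offset deals with early leavers only if dropout is non-informative, and what will be reported if an arm has no events.
4. **Optional.** Have someone other than the assessor receive the returned packaging.

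The cost is a few sentences, recording the dates of events and, if item 4 is adopted, one other person to take the packaging. The drawback is a wide interval that must be read as descriptive.
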